### **6.6.3. Exploratory Analyses**

#### **6.6.3.1. Change in the Subscores of Regional Dimensions (High-level (Shoulder), Distal-level (Wrist and Hand)) of PUL, from Baseline to Week 52**

Summary of the listings and analyses of subscores of regional dimensions (High-level (shoulder), Distal-level (wrist and hand)) of PUL will be summarized for subjects in the ITT population.

The change from baseline to Week 52 in subscores of regional dimensions (High-level (shoulder), Distal-level (wrist and hand)) of PUL, will be analyzed using the same analysis method as the one for the primary endpoint.

#### **6.6.3.2. Change in Duchenne Video Assessment Severity Percentage from Baseline to Week 52**

The Duchenne Video Assessment (DVA) tool provides a standardized way to document and assess patient quality of movement. Caregivers will video record subjects doing specific movement tasks at home using a secure mobile application within 2 weeks prior to the clinic visits specified in the Schedule of Assessments. Trained physical therapists will score the videos in a secure scoring dashboard using scorecards with pre-specified compensatory movement criteria. Casimir, the organization that developed the DVA, will manage DVA data collection, quality, and scoring.

Summary of the listings and analyses Duchenne Video Assessment severity percentage and CGI-C scores will be based on the ITT population. The change from baseline to Week 52 in Duchenne Video Assessment severity percentage will be summarized by analysis visit and analyzed using the MMRM model as described above.

The CGI-C will be analyzed using the proportional odds model, a special case of generalized linear mixed models (GLMM). The GLMM model will include treatment as fixed effect. The model will be fitted using GLMM with a multinomial distribution and a cumulative logit link function. The proportional odds ratio estimate between Pamrevlumab and placebo, the corresponding 95% CI and P-value will be presented. If the proportional odds assumption is contradicted ( $p < 0.05$  in Score Test for the Proportional Odds Assumption) by the observed data, the GLMM method will be replaced by the nonparametric van Elteren test to test whether there is a difference in the location of distribution of the CGI-C at 52 weeks between Pamrevlumab and placebo.

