6.2.7. Duchenne Video Assessment

The Duchenne Video Assessment (DVA) tool provides a standardized way to document and assess patient quality of movement. Caregivers will follow a standardized script to video record subjects doing specific movement tasks remotely using a secure mobile application within 2 weeks prior to the clinic visits specified in the Schedule of Assessments.

Trained physical therapists will score the videos in a secure scoring dashboard using scorecards with pre-specified compensatory movement criteria. The DVA vendor is the organization that developed the DVA and will manage DVA data collection, quality, and scoring.

Caregivers will register for the study mobile application, and they will download the mobile application on an Apple (IOS 10+) or Android (5.1+) smartphone. They will be provided with an eligible smartphone if they do not have access to one. Caregivers will be provided with training materials in the study mobile application and in the study kit (materials provided to each subject and caregiver) to learn how to video record the assigned movement activities. The training materials will describe how to standardize the lighting, clothing, and set-up during the video recording and how to submit videos securely to study staff using the study mobile application. Caregivers will provide an electronic signature within the study mobile application to document training completion.

Subjects will be assigned movement tasks based on functional branching questions prior to Baseline data capture and split into two functional groups based on their Brooke score as noted below. Subjects will remain in the same subgroup (Group A or B) throughout the duration of the study.

Group A: Early Non-Ambulatory Subjects (Brooke Score 1-3)	Group B: Late Non-Ambulatory Subjects (Brooke Score 4-5)
Raise Hands Above Head (Front View and Side View) Take a T-Shirt Off and Put it Back On Eat 10 Bites Roll Over in Bed Sit Up (Shift Weight) in Bed Caregiver Choice New Ability	Eat 10 Bites Putting Arms on Armrest Reach Across Table to Grab Cell Phone Sit up (shift Weight) in Bed Caregiver Choice New Ability

The specific movement activities are detailed in the Caregiver Manual. Caregivers will be provided with study supplies, including painter's tape, tape measure, and a bed wedge.

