In addition to assigned movement tasks, all subjects will complete one caregiver choice activity and new ability videos (if applicable). The caregiver choice activity is an activity that the caregiver will select prior to Baseline data capture that the subject is struggling with, and the caregiver will video record the same caregiver choice activity throughout the study. If caregivers observe the subject gaining a new ability during the study, they can video record the new ability at any time during the study in the study mobile application.

The DVA vendor study staff will monitor data collection to ensure that each video meets quality standards. If videos need to be re-recorded, caregivers will be contacted about re-recording the video.

NOTE: Belgium and China Only: Duchenne Video Assessments will be not be conducted. DVA vendor services and their mobile application will not be used in these countries. There is no alternative for the DVA. All references to DVA or the DVA vendor in the study protocol are not applicable for Belgium and China.

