### 6.6.2.2.3. Covariance Structure Strategy

The unstructured covariance structure for the within-patient errors in the model will be applied first. The by-treatment-group option may will be added to the covariance pattern to improve the model fit as appropriate.

If the algorithm for unstructured covariance pattern does not converge, the following covariance structures will be tested in sequence until the model converges: heterogeneous Toeplitz, homogeneous Toeplitz, first-order autoregressive, compound symmetry, and variance component, until the model converges. The sandwich estimator will be used if there is convergence issue. If the model doesn't converge for all covariance structures listed above, some least significant factors or interaction terms ( $p > 0.05$ ) can be excluded from the model to achieve convergence. The revised model with fewer factors or interaction terms will be tested using the same sequence as specified above.

Sample SAS code:

*/\* excluding baseline visit \*/*

```
PROC MIXED DATA=MMRM (WHERE=(AVISITN>0));
  CLASS TRTP AVISIT;
  MODEL CHG = TRTP AVISIT TRTP*AVISIT BASE /DDFM=KR;
  REPEATED AVISIT /SUBJECT=SUBJID TYPE=UN GROUP=TRTP;
  LSMEANS TRTP /PDIFF CL;
  LSMEANS TRTP*AVISIT /PDIFF CL;
  ODS OUTPUT LSMEANS=MIXLSMNS DIFFS=MIXDIFS;
RUN;
```

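### DVA Groups A and B are scored on different, partly overlapping task sets, but SAP 6.6.3.2 pools them in one MMRM with no group term, which costs precision and makes the pooled effect depend on the A/B mix

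*SAP*

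**What the plan says.** Protocol 6.2.7 says that boys are "split into two functional groups based on their Brooke score". Group A is Brooke 1 to 3 and Group B is Brooke 4 to 5. Inclusion criterion 5 caps Brooke at 5, so every boy falls in one or the other. The grouping does not change later: "Subjects will remain in the same subgroup (Group A or B) throughout the duration of the study".

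SAP 6.6.3.2 analyses one outcome for all ITT boys: the change in "severity percentage will be summarized by analysis visit and analyzed using the MMRM model as described above". It does not say which MMRM. Two appear earlier in the SAP:

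- **SAP 6.6.2.2.3** (grip strength): "MODEL CHG = TRTP AVISIT TRTP*AVISIT BASE /DDFM=KR", that is, one continuous baseline term.
- **SAP 6.6.1.2.1.5** (PUL sensitivity analysis): the text names baseline values as covariates, but the code uses the PUL entry item, `ItemAgrp`, as a class effect.

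Neither contains DVA group. SAP 6.6.4 names no Brooke or DVA-group subgroup and applies its subgroups to PUL and the secondary endpoints. Protocol 8.3.5 gives no DVA model. Protocol 3.4.1 and SAP 3.4 describe 1:1 allocation and state no stratification. Neither document gives the formula for the severity percentage or says that the two task sets are put on a common scale.

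**The concern.** A baseline covariate adjusts properly only if a given value means the same for every boy. Here the percentage comes from one task list in Group A and another in Group B. Two boys with the same baseline percentage may therefore differ in function and in expected one-year change. If mean change differs between groups, that difference sits in the residual variance of a model without a group term. If the treatment effect differs between groups, the pooled estimate is an average weighted by enrolment.

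The SAP accepts this principle for its primary endpoint. Section 7 cites 12-month PUL changes of -0.84 at entry score 1 and -2.05 at entry score 3, and the primary model in 6.6.1.1.5 adjusts for entry score. What is at stake for the DVA is the precision and readability of an exploratory result.

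**Working it through.** **The plan's own figure.** The documents size the trial only for PUL (difference 2.0, SD 2.9, two-sided 0.05, 90% power, 92 boys). The normal approximation gives 45 per arm, 90 in total. The exact t-test gives 90.5% power at 46 per arm and 87.0% at 41 per arm, so the stated 92 and the 87% in SAP section 7 reproduce. There is no DVA sizing figure, and nothing below depends on this one.

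**Task sets** (Protocol 6.2.7, leaving out caregiver choice and new ability, which both groups have):

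- Only in A (3): hands above head, T-shirt, rolling over.
- Only in B (2): arms on armrest, reaching for the phone.
- In both (2): eating, sitting up in bed.

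That makes 5 assigned tasks in A and 4 in B, with 2 shared.

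**Variance carried by the group gap.** Assume an even split, and let d be the A/B gap in mean change, in within-group SDs, that the planned covariate does not absorb. The residual variance without a group term is 1 + 0.25d², so a group term removes 0.25d² / (1 + 0.25d²):

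- d = 0.5: 0.0625/1.0625 = 5.9%. SE factor sqrt(1/1.0625) = 0.970, about 3% smaller.
- d = 1.0: 0.25/1.25 = 20%. SE factor sqrt(1/1.25) = 0.894, about 11% smaller.

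These percentages do not depend on n. The range for d is an assumption. The only related figure in the documents is for PUL: (2.05 - 0.84)/2.9 = 0.42 SD, which is an analogy and not a DVA estimate.

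**Chance imbalance is the same variance.** With the planned 46 per arm, the between-arm difference in the share of Group A has SD sqrt(2 × 0.25/46) = 0.104. At d = 1 that shifts the estimate by 0.104 SD. The SE is sqrt(2 × 1.25/46) = 0.233 without a group term and sqrt(2/46) = 0.209 with one. The difference in quadrature is sqrt(2 × 0.25/46) = 0.104, the same quantity. It is already inside the confidence interval and must not be added to the variance effect.

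**Simulation.** A Week 52 ANCOVA stood in for the MMRM contrast with complete data, with 1,500 runs per setting. All values are assumed: 80 boys, residual SD 10 points, baseline slopes -0.3 in A and +0.1 in B, equal mean baselines (so baseline absorbs none of the gap), a common effect of 6.5 points, and 30%, 50% or 70% in Group A.

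| A/B gap in mean change | Power, pooled | Power, with group terms | SE ratio, pooled to group |
|---|---|---|---|
| 0 | 0.79-0.81 | 0.78-0.82 | 1.00-1.01 |
| 5 points (0.5 SD) | 0.78 | 0.80-0.81 | 1.03-1.04 |
| 10 points (1.0 SD) | 0.71-0.73 | 0.81 | 1.10-1.12 |
| 20 points (2.0 SD) | 0.51-0.57 | 0.80-0.82 | 1.35-1.41 |

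With no treatment effect, the rejection rate was 0.037 to 0.060 over both models, with no pattern. The Monte Carlo standard error is sqrt(0.05 × 0.95/1500) = 0.006.

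**Meaning of the pooled effect.** With an assumed effect of 10 points in A and none in B, the pooled estimate was 2.97, 5.03 and 7.05 points at 30%, 50% and 70% in Group A. That is simply the share in A times 10.

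**The case against.** The case against is substantial, and most of it limits the point rather than removing it.

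- **Two different scales.** A reader might infer that A and B scores lie on two scales. The documents do not show this. The scoring formula is absent, the vendor manages scoring, and normalisation across task sets can be neither confirmed nor excluded. What stands is that no common scaling is stated.
- **One common baseline slope.** This holds only if SAP 6.6.2.2.3 is the model meant. Under the code in 6.6.1.2.1.5 the covariate is baseline arm function by PUL entry item, which may absorb part of an A/B difference. Neither reading has a group term, and the ambiguity itself needs correcting.
- **Validity.** A reader might infer bias or false positives from a chance imbalance between arms. Groups are set before baseline and kept, each boy's change uses his own assigned set, and allocation is random. The test is valid either way.
- **Caregiver choice.** This task varies from boy to boy within a group, so a group term does not give everyone the same tasks. That is true, but the group term still accounts for the systematic difference between the assigned lists.
- **Covariates alone still average A points with B points.** This stands, and is why the treatment difference should also be shown by group.
- **Status.** The endpoint is exploratory and outside the test sequence in SAP Table 1. The subgroup list in 6.6.4 is open-ended, so by-group results are not ruled out, but they are not planned either.

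**Conclusion.** The point holds as a low-cost improvement to an exploratory analysis. The pooled DVA model omits a factor that defines which tasks each boy performs and that is known before baseline. Type I error is unaffected. The loss is precision (about 6% to 20% of variance, or 3% to 11% of the standard error) and a pooled effect that cannot be read without the A/B mix.

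The size rests on an assumed even split and a gap of 0.5 to 1.0 SD, neither of which the documents give. It shrinks if the planned covariate absorbs part of the gap, and vanishes if A and B change equally. The 46 per arm is the planned whole-trial number. Protocol 6.2.7 excludes Belgium and China from the DVA, so any boys enrolled there must be taken off. No confirmatory conclusion of the trial depends on this.

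**What to change.** In SAP 6.6.3.2:

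1. Replace the cross-reference with the MMRM of SAP 6.6.2.2.3, using the baseline DVA severity percentage as the covariate.
2. Add DVA group (A/B), group-by-visit and group-by-baseline terms.
3. Report the by-visit summaries and the Week 52 treatment difference by group beside the pooled estimate. The by-group differences need a separate fit in each group, or a supplementary model with treatment-by-group terms.
4. State how the severity percentage is computed in each group. If the scoring manual puts the two task sets on a common scale, cite it there.

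The cost is SAP wording and a few degrees of freedom. The group is fixed before baseline, so no new data are needed and the terms can be specified while the trial is blinded. By-group estimates will be imprecise and should be labelled descriptive.

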#### **6.6.3.3. Change in Percent Predicted Forced Expiratory Volume at 1 Second (ppFEV1) from Baseline to Week 52**

Standardized PFTs including FVC, PEF, FEV1 will be collected for consistency during the course of the study. The PFT vendor will provide the SpiroSphere®. Within a PFT session, eight attempts may be made. Only sessions with Best Test Read (BTR) grade of borderline or acceptable are considered valid. The session may be repeated up to three times during the screening window. The Day 1 PFT session may also be repeated up to three times. If sessions are repeated, the last session conducted for screening, and the last session conducted for Day 1 supersede all others and are used to determine the average for baseline.

Summary of the listings and analyses percent predicted forced expiratory volume at 1 second (ppFEV1) will be based on the ITT population. The change from baseline to Week 52 in ppFEV1 will be summarized by analysis visit and analyzed using the RCM model as described above.

#### **6.6.3.4. Change in percent predicted peak expiratory flow (ppPEF) from baseline to Week 52, assessed by spirometry**

The change from baseline to Week 52 in ppPEF between two treatment arms will be summarized by analysis visit and analyzed using the RCM model as described above.

**6.6.3.5. Analysis of Progression of Dilated Cardiomyopathy (DCM) by genetic analysis**

A whole blood sample will be collected in a PAXgene blood DNA tube for DNA analysis on Day 1 before dosing for all subjects who agree to DNA analysis (to include but not limited to LTBP4 & SPP1). This testing is optional, requires specific consent by participating subjects and subjects may refuse DNA testing. In the event that a subject later agrees to genetic testing, a blood sample may be collected as an unscheduled lab draw. Only tests for genetic loci associated with dilated cardiomyopathy (DCM) will be performed and all samples will be destroyed after testing is completed.

Summary of the progression of dilated cardiomyopathy (DCM) by genetic analysis will be based on the ITT population. Proportion of patients with progression of dilated cardiomyopathy (DCM) will be summarized.

**6.6.3.6. Fibrosis/MRI assessments:****6.6.3.6.1. Changes in Fibrosis Score of the Biceps Brachii from Baseline to Week 52, Assessed by MRI**

Summary of the listings and analyses of upper arm (bicep) muscle fibrosis assessed by MRI, will be summarized based on ITT population.

The change from baseline to Week 52 in fibrosis score of the biceps brachii muscle assessed by MRI between two treatment arms will be compared by ANCOVA. The ANCOVA model will contain terms for treatment and baseline measurements.

**6.6.3.6.2. Changes in Cardiac Fibrosis Score from Baseline to Week 52, Assessed by Late Gadolinium Enhancement (LGE).**

Summary of the listings and analyses of changes in cardiac fibrosis (LGE) will be based on the ITT population.

The change from baseline to Week 52 in cardiac fibrosis score assessed by MRI and Mass of Late Gadolinium Enhancement (Scar Mass) between two treatment arms, will be compared by ANCOVA. The ANCOVA model will contain terms for treatment and baseline measurements.

In addition, dichotomous responder analysis (proportion of patients with change from baseline in cardiac fibrosis score  $\geq 0$  at Week 52) will be summarized and analyzed. The logistic regression model will be used to compare the proportion of subjects with change from baseline in cardiac fibrosis  $\geq 0$ . The model will include treatment and baseline cardiac fibrosis score.

**6.6.3.7. Change in Myocardial Circumferential Strain [Global Circumferential Strain (GCS)%] percentage from Baseline to Week 52, Assessed by cardiac MRI.**

Summary of the listings and analyses of annual changes from baseline for the Global Myocardial Circumferential Strain (GCS) will be summarized for subjects in the ITT population,

The change from baseline to Week 52 in GCS score between two treatment arms will be compared by ANCOVA. The ANCOVA model will contain terms for treatment and baseline measurements.

In addition, dichotomous responder analysis (proportion of patients with change from baseline in GCS score  $\geq 0$  at Week 52) will be summarized and analyzed. The logistic regression model will

be used to compare the proportion of subjects with change from baseline in GCS score  $\geq 0$ . The model will include treatment and baseline cardiac fibrosis score.

